6.2.1. Rationale for Exclusion of Certain Study Candidates

The safety, tolerability, and PK of LY3316531 are being assessed in female subjects as part of Study FFAA. As Study FFAB is focused only on the ability of LY3316531 to neutralize CGRP, the evaluation specifically in female subjects is not needed. Female subjects are being excluded from Study FFAB to avoid the demonstrated hormone-dependent variations in CGRP-mediated DBF previously found in healthy females (Ibrahimi et al. 2017).

6.3. Lifestyle and/or Dietary Requirements

Throughout the study, subjects may undergo medical assessments and review of compliance with requirements before continuing in the study.

6.3.1. Meals and Dietary Restrictions

Subjects should not eat after midnight during the night before study drug administration. Water is permitted. Subjects may eat breakfast approximately 2 hours postdose. A normal diet may be consumed at all other times during the study.

6.3.2. Caffeine, Alcohol, and Tobacco

6.3.2.1. Caffeine and Alcohol

The use of caffeine-containing products and/or alcohol is not allowed from 24 hours prior to all study visits and during in-clinic stays. At all other times, alcohol consumption is limited to no more than 2 alcoholic beverages or equivalent (beer [284 mL/10 ounces], wine [125 mL/4 ounces], or distilled spirits [25 mL/1 ounce]) per day and caffeinated beverages will be limited to no more than 2 units (1 unit = 120 mg of caffeine) per day.

6.3.2.2. Tobacco

Subjects will be excluded if they have used cigarettes or other tobacco products within 3 months prior to the start of this study.

6.3.3. Activity

Strenuous activity is not allowed within 48 hours prior to admission on Day -1 and 48 hours prior to each visit.

6.3.4. Contraception

All subjects and their partners should agree to use a reliable method of birth control during the study and for 5 months following dosing of the study drug (see Inclusion Criterion [2]).

6.4. Screen Failures

Healthy subjects who do not meet the criteria for participation in this study (screen failure) may not be re-screened. However, if, for example, a subject had an intercurrent illness around the time of initial screening or there are issues with the quality of the laboratory safety samples (eg, hemolysis), re-assessment of laboratory parameters including drug screen and vital signs will be allowed.

In addition, participants who were eligible for inclusion in previous cohorts, but were not randomized for nonmedical reasons, may be reassessed, following a discussion with the sponsor.

7. Treatment

7.1. Treatment Administered

LY3316531 is supplied for clinical trial use as solution formulation in glass vials. Further dilution may be needed for IV administration. See Pharmacy Instructions for more information.

Placebo will be sterile saline (0.9% NaCl). Placebo doses should be held in the pharmacy for an equivalent amount of time as is required to prepare doses of LY3316531.

The IP will be administered as a slow IV infusion over at least 30 minutes. Sites must have resuscitation equipment, emergency drugs, and appropriately trained staff available during the infusion and for at least 6 hours after subjects have completed receiving their infusion.

All clinical trial materials provided to the investigator will be stored in a secure place, assigned using the interactive web response system, and dispensed by appropriately trained persons. The dispensing of the IPs will be fully documented. Detailed records of the amounts of the IP received, dispensed, and remaining at the end of the study will be maintained.

The investigator or designee is responsible for

- explaining the correct use of the IP(s) to the site personnel
- verifying that instructions are followed properly
- maintaining accurate records of dispensing and collecting IP, and
- returning all unused IP to Lilly or its designee at the end of the study.

Note: In some cases, sites may destroy the material if, during the investigative site selection, the evaluator has verified and documented that the site has appropriate facilities and written procedures to dispose of clinical materials.

The products for the capsaicin and the vehicle solutions required for the capsaicin-induced DBF assessment will be supplied by the investigative site. Pharmacy instructions for the preparation of these capsaicin and vehicle solutions will be provided by the investigative site.

7.1.1. Packaging and Labeling

LY3316531 and Pbo will be supplied to the investigative site by Lilly or its designee in accordance with current good manufacturing practices, and will be supplied with lot numbers, expiry dates, and certificates of analysis, as applicable.

Clinical trial materials will be labeled according to the country's regulatory requirements. All IPs will be stored, inventoried, reconciled, and destroyed according to applicable regulations. Clinical trial materials are manufactured in accordance with current good manufacturing practices.

LY3316531 is supplied for clinical trial use as solution in vial with study-specific labels. The 2-mL vial is manufactured to contain 150 mg of LY3316531 (75 mg/mL). Vials will be supplied in cartons, with the appropriate quantity specific to the planned dispensing schedule of the IP.

Placebo for all cohorts is 0.9% sodium chloride (sterile saline).

When prepared for dosing according to instructions, it will not be possible to distinguish between LY3316531 and Pbo.

The IP must be prepared by an unblinded pharmacist who is not involved in any other study-related procedures.

7.2. Method of Treatment Assignment

Randomization tables for allocation of LY3316531 or Pbo will be prepared by the statistician or designee for the study and provided to the site pharmacists involved in dose preparation.

The allocation and dispensation of the IP will be fully documented and verified by a second person. Detailed records of the amounts of the IP received, dispensed, and remained at the end of the study will be maintained by the site pharmacy.

7.2.1. Selection and Timing of Doses

The dose in Cohort 1 will be 300 mg of LY3316531 administered through IV infusion. The actual time of the single dose administered to each subject will be determined by the site and recorded in each subject's case report form (CRF).

A decision to implement the optional Cohort 2 will be made if a statistically significant decrease in capsaicin-induced DBF (relative to placebo) is not seen with 300 mg (Cohort 1) within 9 days of the dose (Day 10). If Cohort 2 is conducted, the single dose not to exceed 2000 mg or the highest tolerable dose determined to be safe in Study FFAA will be administered through IV infusion over the same time period as used in Cohort 1.

7.3. Blinding

Study FFAB will be subject- and investigator-blind. Pharmacy staff who prepare and dispense study medication are required to be unblinded to treatment allocation and are not allowed to participate in any other procedure of this study. Subject treatment assignments and drug accountability records will be held in a secure location accessible only by individuals involved with study drug preparation or dispensation. Blinding will be maintained throughout the conduct of the study as described in the separate Blinding Plan.

In case of an emergency, appropriate site personnel per the site's standard operating procedure have the sole responsibility for determining if unblinding of a subject's treatment assignment is warranted for medical management of the event. The subject's safety must always be the first consideration in making such a determination. If the investigator decides that unblinding is warranted, it is the responsibility of the investigator to promptly document the decision and rationale and notify Lilly as soon as possible.

Upon completion of the study, all codes must be returned to Lilly or its designee.

7.4. Dose Modification

7.4.1. Special Treatment Considerations

7.4.1.1. Management of Infusion Reactions

Infusion-related reaction (IRR) is a risk with any biological agent; therefore, all subjects should be monitored closely for IRR. Symptoms and signs that may occur as part of an IRR include, but are not limited to fever, chills, nausea, headache, bronchospasm, hypotension, angioedema, throat irritation, rash, pruritus, myalgia, and dizziness. In the event that a significant IRR occurs, the following guidance should be followed:

- The infusion should be slowed (for example, reduce infusion rate by 50% [for example, an infusion rate of 12 mL/hour becomes 6 mL/hour or slower]) or stopped, depending on the symptoms/signs present:
 - if slowed, the infusion should be completed at the slower rate, as tolerated
 - if determined by the investigator that the infusion should no longer continue, no further attempts to dose the subject should be made
- Supportive care should be employed in accordance with the symptoms/signs
- Premedication for the infusions is not planned. However, if an IRR occurs in previously-dosed subjects, appropriate pre-medication (for example, acetaminophen 500 to 1000 mg and/or an antihistamine administered orally 30 to 60 minutes prior to the start of infusion) may be administered to subsequently-dose subjects as determined by the study investigator(s). The decision to premedicate for infusions will be made by the investigator and sponsor and recorded in the study documentation. Any premedications given will be documented as a concomitant therapy (see Section 7.7).

7.5. Preparation/Handling/Storage/Accountability

LY3316531 vials should be stored at 2°C to 8°C (36°F to 46°F) in the original carton to protect it from light. LY3316531 vials should not be frozen.

Sterile saline vials (0.9% sodium chloride) should be stored at room temperature (15°C to 25°C [59°F to 77°F]). The investigator or designee must confirm appropriate temperature conditions have been maintained, as communicated by Sponsor, during transit for all IPs received and any discrepancies are reported and resolved before use of the study treatment.

All clinical trial materials provided to the investigator will be stored in a secure place and allocated and dispensed by appropriately trained personnel. The allocation and dispensation of the IP will be fully documented and verified by a second person. Detailed records of the amounts of the IP received, dispensed, and remaining at the end of the study will be maintained.

Only participants enrolled in the study may receive IPs or study materials, and only authorized site staff may supply or administer IP. All IPs should be stored in an environmentally controlled

and monitored (manual or automated) area in accordance with the labeled storage conditions with access limited to the investigator and authorized site staff.

Detailed instructions for the preparation and handling of LY3316531 will be provided by the sponsor.

The IP must be prepared by an unblinded pharmacist who is not involved in any other study related procedures.

All IPs will be stored, inventoried, reconciled, and destroyed according to applicable regulations. Clinical trial materials are manufactured in accordance with current good manufacturing practices.

Detailed records of the amounts of the IP received, dispensed, and remained at the end of the study will be maintained by the site pharmacy.

The investigator, institution, or the head of the medical institution (where applicable) is responsible for study treatment accountability, reconciliation, and record maintenance (such as receipt, reconciliation and final disposition records).

The investigative site will be responsible for obtaining United States Pharmacopeia (USP) and The National Formulary-grade capsaicin, performing analysis to demonstrate compliance with USP, and handling and storing the capsaicin powder in accordance with the manufacturer instructions. The site will be responsible for preparing, handling, and storing the capsaicin solution to be used in the capsaicin challenges in accordance with the manufacturer instructions.

7.6. Treatment Compliance

The IP will be administered at the clinical site, and documentation of treatment administration will occur at the site.

7.7. Concomitant Therapy

In general, concomitant medication should be avoided unless required to treat an AE.

The use of chronic, stable doses of thyroxine is allowed. The use of multivitamins and vitamin C is allowed until 2 days prior to entrance into the CRU. The use of acetaminophen (paracetamol), up to 2 grams per day, is allowed up to 3 days before entrance into the CRU. Thereafter and during the study the investigator may permit a limited amount of acetaminophen for the treatment of headache or any other pain.

Other medication to treat AEs will be prescribed according to the circumstances and guided by the investigator's judgment. If the need for concomitant medication (other than acetaminophen) arises, inclusion or continuation of the subject will be at the discretion of the investigator and Lilly clinical pharmacologist or CRP. In the event medication is used, the name of the drug, the dose and dosage regimen will be recorded in the CRF.

7.8. Treatment after the End of the Study

This section is not applicable to this study.

8. Discontinuation Criteria

8.1. Discontinuation from Study Treatment

8.1.1. *Discontinuation of Inadvertently Enrolled Subjects*

If the Sponsor or investigator identifies a subject who did not meet enrollment criteria and was inadvertently enrolled, the subject must be discontinued from the study.

8.2. Discontinuation from the Study

Subjects will be discontinued in the following circumstances:

- Enrollment in any other clinical study involving an IP or enrollment in any other type of medical research judged not to be scientifically or medically compatible with this study
- Participation in the study needs to be stopped for medical, safety, regulatory, or other reasons consistent with applicable laws, regulations, and good clinical practice (GCP)
- Investigator Decision
 - the investigator decides that the subject should be discontinued from the study
 - if the subject, for any reason, requires treatment with another therapeutic agent that has been demonstrated to be effective for treatment of the study indication, discontinuation from the study occurs prior to introduction of the new agent
- Subject Decision
 - the subject, or legal representative, requests to be withdrawn from the study.
- Sponsor Decision
 - Lilly stops the study or stops the subject's participation in the study for medical, safety, regulatory, or other reasons consistent with applicable laws, regulations, and GCP
- Adverse event
 - A clinically significant systemic hypersensitivity reaction occurs following administration of the IP (for example, drug-related symptomatic bronchospasm, allergy-related edema/angioedema, or hypotension) that requires parenteral medication, does not respond to symptomatic medication, or results in clinical sequelae or an anaphylactic reaction.

The nature of any conditions, clinical signs or symptoms, or abnormal laboratory values present at the time of discontinuation and any applicable follow-up procedures will be documented.

Refer to the Schedule of Activities (Section 2) for data to be collected at the time of discontinuation and follow-up.

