- For galcanezumab, as of November 2017, 3156 clinical trial participants (419 healthy subjects, 2586 patients with migraine, and 151 patients with osteoarthritis) have been exposed to galcanezumab. Galcanezumab single doses ranged from 1 to 600 mg and multiple doses were up to 300 mg. The Phase 3 clinical studies in patients with migraine demonstrated clinically meaningful reductions in migraine headache days and a favorable safety profile that includes a low incidence of serious adverse events (SAEs) and discontinuations due to adverse events (AEs). Treatment-emergent adverse events (TEAEs) were generally mild to moderate. A total of 1 serious adverse reaction (urticaria) has been reported.

Because LY3316531 has been administered only as single doses to relatively few human subjects and only 6 of these subjects were dosed as high as 300 mg (Study FFAA), Study FFAB has been designed to be conducted in accordance with principles outlined in the Guideline on Strategies to Identify and Mitigate Risks for First-in-Human Clinical Trials with Investigational Medicinal Products (EMA/CHMP/SWP/28367/07 Rev. 1).

No clinically significant adverse events or changes in laboratory safety parameters (hematology, clinical chemistry urinalysis), vital signs, or ECGs occurred in the ongoing Study FFAA. LY3316531 was administered as single IV ascending doses (3, 15, 75 and 300 mg) in a total of 18 healthy male and female subjects (Part A, Cohorts 1 through 4). Safety data from the 300-mg

IV Cohort 4 (6 subjects) in Study FFAA were reviewed and found acceptable for dosing at 300-mg IV in Study FFAB.

Study FFAA has additional cohorts planned for a single 300-mg SC dose and up to 2000-mg IV doses in healthy subjects (Part A) and multiple IV doses in healthy subjects (Part B), with each subject evaluated over a 3-month period. Also planned are a single-dose 300-mg cohort and 2 optional single-dose cohorts (dosage to be determined) in patients with psoriasis (Part C) pending analysis of safety data across all previous cohorts.

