5.1. Overall Design

[figure not shown]
Study FFAB is a Phase 1 single-site, randomized, subject- and investigator-blind, placebo (Pbo)-controlled, parallel-dose group, single-dose study of LY3316531 in healthy subjects.

After a screening period up to 28 days, subjects will be admitted to the clinical research unit (CRU) on Day -1 and will fast overnight. Subjects will receive a single dose of study drug or Pbo on Day 1 and will undergo the study assessments specified in the Schedule of Activities (Section 2). Subjects may be discharged on Day 2, up to 32 hours after dose administration. In case of safety concerns, subjects will be required to stay in the CRU for a longer period at the discretion of the investigator. Subjects will return to the CRU during the postdose follow-up period (Visits 3 through 10) for a total of 8 follow-up visits through Day 160. For each follow-up visit, subjects will attend the CRU to have the capsaicin challenge and LDI measurement performed along with any other scheduled procedures. These visits are specified in the Schedule of Activities (Section 2) and [Figure FFAB.1](#).

The study will evaluate 1 cohort of 16 subjects (12 LY:4 Pbo) with a planned single dose of 300-mg LY3316531 via IV administration. If no treatment effect on DBF is detected in Cohort 1, an optional Cohort 2 (12 subjects; 9 LY:3 Pbo) may be evaluated with a dose not to exceed 2000-mg IV or the highest tolerable dose determined to be safe in the single-ascending dose (SAD) Study FFAA. The decision to implement the optional Cohort 2 will be made if a sufficiently large decrease from baseline, relative to placebo, in capsaicin-induced DBF is not seen with 300 mg (Cohort 1) within 9 days of the dose (on Day 10). Both cohorts will follow the same admission, treatment, and assessment schedule.

Subjects enrolled will be followed for up to 160 days post treatment administration. It is not planned to replace subjects; however, subjects may be replaced if necessary to meet study objectives or at the discretion of the Sponsor.

Study governance considerations are described in detail in [Appendix 3](#).

Abbreviations: D = day; V = visit.

Figure FFAB.1. Protocol I9H-MC-FFAB study design for Cohort 1 and optional Cohort 2.

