5.4. Scientific Rationale for Study Design

This study will assess the pharmacodynamic effects of LY3316531 using capsaicin challenge and LDI over 160 days following the single dose. In addition, the PK, safety, and tolerability of a single dose of LY3316531 will be evaluated.

A parallel-group design (drug versus Pbo) was selected based on the expected long half-life of the molecule in humans.

For operational reasons, dosing may be conducted in smaller groups, for example, 4 subjects (3 LY, 1 Pbo) per day.

Subjects will remain in the CRU for up to 32 hours after the single dose of LY3316531 or Pbo at Visit 2 to provide adequate and close safety monitoring and to allow for a 24-hour postdose capsaicin challenge and LDI measurement.

Follow-up visits will occur on Day 10 (Visit 3) and approximately every 14 days thereafter for Visits 4 through 8. Visits 9 and 10 will occur at Day 120 and Day 160, respectively. LDI measurements and follow-up visits will continue up to Day 160 based on the long duration of the PD effect noted in this study (see Schedule of Activities in Section 2).

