Non-Human Primates NOAEL^c		200 QW	5	371250	1.3	6358	5.3

Abbreviations: AUC = area under the plasma concentration versus time curve; C_{max} = maximal observed drug plasma concentration; NOAEL = no-observed-adverse-effect level; PK = pharmacokinetics; QW = once per week.

^a Dose multiple is the dose in animals/dose in humans based on mg/kg. AUC exposure multiple = mean AUC_{tau} observed after the last dose in monkeys/predicted mean $\text{AUC}(0-\infty)$ after a single dose in humans. C_{max} exposure multiple = mean C_{max} observed after the last dose in monkeys/predicted mean C_{max} after a single dose in humans.

^b Body weight of human is based on the lowest permitted body weight (50 kg) for Study FFAB. Human PK parameters were predicted using allometric scaling methods based on data collected following a single dose of LY3316531 in monkeys (Study 8340704).

^c NOAEL determined in a 3-month repeat-dose toxicity study in monkeys (Study #20108516).

6. Study Population

Eligibility of subjects for the study will be based on the results of screening medical history, physical examination, vital signs, chest x-ray, clinical laboratory tests, and electrocardiogram (ECG).

The nature of any conditions present at the time of the physical examination and any preexisting conditions will be documented.

Screening may occur up to 28 days prior to enrollment. Subjects who are not enrolled within 28 days of screening may be subjected to an additional medical assessment and/or clinical measurements to confirm their eligibility.

Prospective approval of protocol deviations to recruitment and enrollment criteria, also known as protocol waivers or exemptions, is not permitted.

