9.2. Adverse Events

Investigators are responsible for monitoring the safety of subjects who have entered this study and for alerting Lilly or its designee to any event that seems unusual, even if this event may be considered an unanticipated benefit to the subject.

The investigator is responsible for the appropriate medical care of subjects during the study.

Investigators must document their review of each laboratory safety report.

The investigator remains responsible for following, through an appropriate health care option, AEs that are serious or otherwise medically important, considered related to the IP or the study, or that caused the subject to discontinue the IP before completing the study. The subject should be followed until the event resolves, stabilizes with appropriate diagnostic evaluation, or is reasonably explained. The frequency of follow-up evaluations of the AE is left to the discretion of the investigator.

After the informed consent form (ICF) is signed, study site personnel will record, via electronic case report form (eCRF), the occurrence and nature of each subject's preexisting conditions, including clinically significant signs and symptoms of the disease under treatment in the study. Additionally, site personnel will record any change in the condition(s) and the occurrence and nature of any AEs.

The investigator will interpret and document whether or not an AE has a reasonable possibility of being related to study treatment or a study procedure, taking into account the disease, concomitant treatment or pathologies.

A "reasonable possibility" means that there is a potential cause and effect relationship between the IP, study device and/or study procedure and the AE.

Planned surgeries should not be reported as AEs unless the underlying medical condition has worsened during the course of the study.

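### Section 8.1.1 takes an already-dosed ineligible subject out of the study, leaving one early-discontinuation visit in place of the remaining scheduled safety, PK and ADA visits (same structure, smaller gap, for hypersensitivity in 8.2)

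*Protocol*

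**What the plan says.** Section 8.1 of the protocol is headed as discontinuation from study treatment. Its only rule, 8.1.1, is about leaving the study: once a subject is found to have been "inadvertently enrolled, the subject must be discontinued from the study". Appendix 1 defines enrollment as assignment to a treatment, so the rule covers subjects found before dosing and after dosing alike, and does not separate them.

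Section 8.2 lists further circumstances for mandatory exit. One is that "A clinically significant systemic hypersensitivity reaction occurs following administration of the IP" and needs parenteral medication, does not respond to symptomatic medication, or leads to sequelae or anaphylaxis. Such a subject has, by definition, received at least some IP.

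There is one dose. Section 5.1: "Subjects will receive a single dose of study drug or Pbo on Day 1". Eight follow-up visits then run from Day 10 to Day 160.

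On what happens at exit, 8.2 says: "Refer to the Schedule of Activities (Section 2) for data to be collected at the time of discontinuation and follow-up". The Schedule has one ED column (physical examination, vital signs, ECG, AE review, laboratory tests, PK, ADA, total CGRP, and a conditional capsaicin challenge) and no column after it.

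**The concern.** In a multiple-dose trial, removing an ineligible or reacting subject stops further dosing. Here a completed infusion cannot be undone, and Section 7.4.1.1 already governs stopping one in progress. For a fully dosed subject, study exit therefore buys no reduction in exposure. It spares him capsaicin challenges and blood draws, and it gives up the scheduled AE, laboratory, PK and ADA assessments.

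Some of the entry criteria a subject may turn out to have failed exist to protect safety: latent or active TB (criterion 29), immunocompromise (30), hepatitis B or C or HIV (35). Section 3.3 names reactivation of infection as a risk of this drug and relies on screening to contain it. If such a finding is missed until after dosing, 8.1.1 ends scheduled surveillance in a subject who may have more need of it than the others.

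**Working it through.** **1. Inputs, checked against the plan's own totals.** Assessments counted from the Schedule of Activities (Protocol Section 2), compared with Appendix 5:

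| Assessment | Up to Day 2 | After discharge | Total | Appendix 5 |
|---|---|---|---|---|
| PK | 5 | 8 (V3–V10) | 13 | 13 |
| Chemistry/hematology (after screening) | 2 | 8 (V3–V10) | 10 | 10 |
| Total CGRP | 2 | 8 (V3–V10) | 10 | 10 |
| ADA | 1 | 5 (V3, V4, V8, V9, V10) | 6 | 8 |
| AE review | not needed here | 6 (V3–V8) | – | not a blood sample |

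Three totals agree. Appendix 5 calls its counts approximate; for ADA the Schedule's 5 post-discharge samples are used.

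**2. Scheduled assessments lost.** Net loss = assessments remaining after the last attended visit − 1 (the ED visit).

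| Last attended visit | AE review | Laboratory | PK | ADA |
|---|---|---|---|---|
| Day 2 | 6 − 1 = 5 | 8 − 1 = 7 | 8 − 1 = 7 | 5 − 1 = 4 |
| Day 10 (V3) | 5 − 1 = 4 | 7 − 1 = 6 | 7 − 1 = 6 | 4 − 1 = 3 |
| Day 24 (V4) | 4 − 1 = 3 | 6 − 1 = 5 | 6 − 1 = 5 | 3 − 1 = 2 |

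**3. What survives exit, and what sets it off.**

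- Section 9.2: an AE that is serious, medically important, related or the cause of discontinuation. "The subject should be followed until the event resolves, stabilizes with appropriate diagnostic evaluation, or is reasonably explained". It needs an existing AE.
- Schedule footnote h and Section 9.6.3: up to 3 extra PK and ADA samples, the last 30 days after the event. They need a hypersensitivity reaction.
- Section 9.4.4.1: repeat liver tests and monitoring. It needs ALT, ALP or bilirubin over a threshold, which the ED sample could show.
- Section 9.6.3: further ADA samples, with PK at the titer-driven time points. It needs a rising or high titer at the last or discontinuation visit, or a possibly immune-mediated AE, and is optional even then.
- Section 9.2.1: prompt notification of a possibly related SAE after discharge. It needs the investigator to learn of it; the same section lifts the general duty to follow AEs and SAEs after discontinuation.
- Section 8.2: documentation of conditions present at exit and of applicable follow-up. It creates no visit.

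An 8.1.1 subject with no AE, no liver signal and no high or rising titer at ED sets off none of the active follow-up. Only passive SAE notification remains. A subject leaving for hypersensitivity sets off the first two items, so his gap is smaller.

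**4. Exposure still ahead at exit (context only).** From Table FFAB.5.2 at 300 mg, predicted Cmax is 180 µg/mL and AUC 43,600 µg·h/mL. These are predictions: "Human PK parameters were predicted using allometric scaling methods based on data collected following a single dose of LY3316531 in monkeys". Assuming mono-exponential decline, AUC/Cmax = 43,600/180 = 242 h and half-life = 0.693 × 242/24 = 7.0 days. The fraction of AUC remaining is 50% at 7 days postdose (Day 8), exp(−216/242) = 41% at Day 10 and exp(−552/242) = 10% at Day 24.

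**The case against.** The rule is a defensible choice for healthy volunteers. They expect no benefit (Section 3.3), the ED assessment is broad, and releasing an ineligible volunteer from more challenges and venipunctures is a reasonable courtesy. Section 6 also bars eligibility waivers, so a sponsor may want a firm rule. All of this stands for a subject found ineligible before dosing. For a dosed subject it stands only in part. Keeping him under observation is not an enrollment waiver, the capsaicin challenge can be dropped separately, and the mandatory wording leaves the investigator no choice in the direction of more follow-up.

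Several stronger readings are tempting, and the documents do not support them:

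- *All follow-up ends at exit.* It does not; step 3 of the working lists what continues. For hypersensitivity in particular, much of the relevant follow-up is kept.
- *All of Section 8.2 is at fault.* Withdrawal by the subject, sponsor decision and entry into another study are ordinary exits. Only the hypersensitivity bullet shares the problem.
- *AE surveillance to Day 160 is lost.* Section 5.4 extends the visits "based on the long duration of the PD effect noted in this study", which is a PD reason, and scheduled AE review stops at Day 80 for everyone. Only laboratory, PK and ADA assessments run on to Day 160.
- *Most of the drug exposure is always still to come.* Under the assumption in step 4, that holds only for exit before about Day 8.
- *The subject disappears from the limited 300-mg experience.* He still contributes infusion, 24-hour, attended-visit and ED data.
- *The primary analysis is at risk.* SAP 6.6 tests Visits 3 and 4, so only an exit before Visit 4 matters. Replacement is allowed (Protocol 5.1), and an ineligible subject may be left out of the analysis population anyway (SAP 6.1).

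**Conclusion.** The concern holds, as a minor point, and its proper anchor is 8.1.1. A subject who has had the whole dose and is then found ineligible must leave the study. His remaining scheduled assessments shrink to one of each kind, at a net cost of up to 5 AE reviews, 7 laboratory, 7 PK and 4 ADA assessments, and less the later he leaves. If no trigger is met by the ED visit, a later AE, laboratory change or antibody response is not looked for. The hypersensitivity bullet in 8.2 has the same structure with a smaller gap.

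This rests on the infusion having been completed, on the ED visit taking place, and on the subject being willing to continue. The documents give no rate for either kind of exit; I take both to be rare. The counts in step 2 do not depend on the half-life assumption.

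**What to change.** In 8.1.1, and in the hypersensitivity bullet of 8.2, state that a subject who has received any IP remains in the AE, laboratory, PK and ADA visits already in the Schedule, unless he withdraws consent or the investigator judges continuation unsafe. Leave the capsaicin challenge to the investigator; for example, it would be withheld from someone found to be capsicum-sensitive (criterion 36). Keep mandatory study exit for enrollment errors found before dosing. Appendix 1 counts placebo as IP, so the rule can be applied without breaking the blind.

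The cost is protocol wording and, for rare subjects, visits and draws that the plan already contains. For an exit that would have followed Day 2, Appendix 5 volumes give at most 7 × 12.5 + 7 × 5 + 4 × 7.5 = 152.5 mL of laboratory, PK and ADA blood beyond an ED visit, within the 320 mL already planned per subject.
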